## **7. RESEARCH METHODS**

### **7.1. Study Design**

This is a cohort study using data from the Veterans Affairs National Sample, which is composed of Veterans who receive healthcare services through the Veterans Health Administration (VHA). This national sample is representative of the Veteran population, capturing a wide range of demographic, clinical, and social characteristics.

Data will be extracted from VHA's Corporate Data Warehouse (CDW), a comprehensive, regularly updated repository of information from VHA's electronic health records and administrative files. It includes patient-level data such as demographics, clinical encounters (diagnoses, interventions), laboratory and imaging results, medication details, health services utilization, and long-term health outcomes.

The study period will range from January 1, 2021, to December 31, 2025. Initiation of PrEP regimen will be assessed during the period January 1, 2021 to June 30, 2025, to allow for at least 6 months of observation following PrEP initiation.

The study will include different cohorts, as described in Table 2.

Veterans who are not on PrEP but could benefit from PrEP will be identified based on risk factors for HIV acquisition or factors linked to behaviors increasing the risk of HIV acquisition which are generally documented in Veterans health records. These risk factors include: tested for or diagnosed with a bacterial STI in the past 12 months (gonorrhea, syphilis, chlamydia) (US CDC, 2024), tested for HIV in the past 12 months, ever had alcohol use disorder (Williams, 2016), ever used illicit non-injection drugs (HIV.gov, 2024), ever used injectable drugs (CDC, 2024), Black women (CDC, 2024; Reaves, 2025), men who have sex with men (CDC, 2022; Mayer, 2021), individuals aged 18-24 years (HIV.gov, 2025 b), any history of PrEP use (Hojilla, 2021; Krakower, 2019).

---

 The US CDC recommends PrEP for people with a bacterial STI diagnosis in the past 6 months. This has been extended to testing for a bacterial STI in the past 12 months for this protocol.

**Table 2:** Description of study cohorts

Objectives	Criteria	
Objective 1a - Among all Veterans without evidence of HIV infection	Population/exposure	No evidence of HIV diagnosis at beginning of each calendar year of the study period under analysis
	Index date	N/A
	Censoring criteria	N/A
	Endpoint	HIV diagnosis

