Objective 1b - Among Veterans with a new HIV diagnosis during the study period	Index date	Date of HIV diagnosis
	Censoring criteria	NA
	Endpoint	PrEP use (never, use within 12 months before diagnosis, use >12 months before diagnosis)
Objective set 2 – among Veterans without evidence of HIV infection who are not on PrEP but could benefits from PrEP	Population/exposure	At least one of the following criteria: tested for or diagnosed with a bacterial STI in the past 12 months (gonorrhea, syphilis, chlamydia), tested for HIV in the past 12 months, ever had alcohol use disorder, ever used illicit non-injection drugs, ever used injectable drugs, Black women, men who have sex with men, individuals aged 18-24 years, any history of PrEP use
	Index date	First visit during the study period with criteria indicating the individual could benefit from PrEP
	Censoring criteria	Death, loss to follow-up, end of the study period, 12 months after index date, PrEP initiation, whatever comes first
	Endpoints	HIV testing, HIV diagnosis, Screening/testing for other STIs, STI diagnoses
Objective set 3 – among Veterans with a PrEP prescription	Exposure groups	Oral PrEP, CAB LA PrEP
	Index date	Start of first PrEP regimen during the study period (dispensing date for oral PrEP, injection date for CAB LA)
	Censoring criteria for calculation of proportion of days covered	Death, loss to follow-up (12 months after last clinical contact), study end, 12 months after index date whatever comes first
	Endpoints	Adherence to PrEP schedule, discontinuation and resumption of PrEP, STI screening/testing, STI diagnosis, STI treatment prescription, HIV testing and diagnosis

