**b) Adherence to CAB LA PrEP schedule**

- Proportion of days covered by CAB LA PrEP in the 12 months following initiation: number of days covered by CAB LA PrEP divided by the number of days in the observation period

Follow-up will be censored at first of:

- a) 12 months after index date
- b) Loss to follow-up
- c) Death
- d) Study end

Coverage by LA PrEP will be determined based on the duration of days covered by the medication, according to the label.

- 1st injection: coverage = 37 days (30 days of coverage + 7-day injection window)
- Subsequent injections: coverage = 67 days (60 days of coverage + 7-day injection window)

Each calendar day will only be counted once, even if there is an overlap between coverage from the prior injection and date of the next injection.

- **Complete versus incomplete initiation:**

- Among all Veterans with  $\geq 1$  CAB LA injection:

→ Complete initiation (2nd injection received within 67 days following the 1st injection)

- 2nd initiation injection on time: 2nd injection between 23 and 37 days following the first injection
- 2nd initiation injection late: 2nd injection between 38 and 67 days following the first injection

→ Incomplete initiation: >67 days without injection following the first injection

- Among incomplete initiators

Any additional injection(s) >67 days after the 1st injection (Yes/no)

If yes:

- o Timing of the 1st additional injection after the last injection of the “incomplete initiation” (interval in days, number with interval of 68-97 days and interval >97 days)
- o Complete versus incomplete reinitiation
- o Interval between the first two reinitiation injections ( $\leq 37$ ; 38-67, 68-97, 98-127;  $\geq 128$  days apart)

• **Timing of CAB LA PrEP maintenance injections:** among complete initiators with at least one maintenance injection

Determined based on the time between initiation injections (Table 3)

- Total number of maintenance injections per individual
- All on time
- Any late maintenance injection (short delays not requiring reinitiation, long delays requiring reinitiation): number of short and long delays, number of individuals with 1, 2, 3 or more short delays, number of individuals with 1, 2, 3 or more long delays, median duration of short and of long delays

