**Table 3:** Timing of CAB LA PrEP maintenance injections, among complete initiators with  $\geq$  maintenance injection

Dosing pattern	Timing of maintenance injections (following previous injection)
On-time	53-67 days
Late	68-127 days
Short delay not requiring reinitiation	68-97 days
Long delay requiring reinitiation	98-127 days
Discontinuation	>127 days without injection

◆ **Patterns of PrEP use (Objective 3.4)**

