**b) CAB LA PrEP: among complete initiators with at least one maintenance injection**

- Total number maintenance injections administered during first period of CAB LA PrEP use (overall and by person)

- Total follow-up time for complete CAB LA initiators with at least one maintenance injection (from first CAB LA PrEP injection to study end, loss to follow-up, death or HIV acquisition, whatever comes first)
- Discontinuation: number of individuals discontinuing CAB LA PrEP and number of individuals resuming LA PrEP injections (additional CAB LA or LEN LA injections after discontinuation and time between the last injection prior discontinuation and the first injection post-discontinuation) or oral PrEP
- Oral bridging between discontinuation of CAB LA injections and resumption of CAB LA injections
- Months on regimen until first censoring (first period of CAB LA PrEP use)  
Calculated as: days from first initiation injection to censoring (study end, loss to follow-up, death, HIV acquisition, discontinuation)
- Cumulative months on regimen across all CAB LA PrEP use (including additional injections after discontinuation)
  - Continuous time on CAB LA PrEP will be calculated as:
    - If no discontinuation: days from first initiation injection to censoring (study end, loss to follow-up, death, HIV acquisition)
    - If discontinuation: days from first initiation injection to discontinuation date (i.e., 127 days after last injection)
  - Among individuals with additional injections after discontinuation, the cumulative months on CAB LA regimen will be calculated across all episodes of continuous CAB LA PrEP use
  - Individuals with incomplete initiation of their first period of CAB LA PrEP use will be excluded from this analysis even if they have additional injections after incomplete initiation
- On CAB LA PrEP at timepoints of interest – among CAB LA users with no discontinuation and among CAB LA users with discontinuation
  - 12 months: injection received between  $\geq 238$  to  $\leq 365$  days after index (up to 127 days before the 12-month mark)
  - 24 months: injection received between  $\geq 603$  to  $\leq 730$  days after index (up to 127 days before the 24-month mark)
  - Study end: injection received up to 127 days before or on study end date
- ◆ **HIV testing & STI testing/screening during first period of PrEP use (Objectives 3.5)**
  - HIV testing

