##### **Veterans using PrEP (Objective set 3)**

**Objective 3.1-** Baseline demographic and clinical characteristics will be described at the start of PrEP use during the study period, by regimen type (oral or CAB LA), using median and interquartile ranges for continuous variables and counts and proportions for categorical variables.

**Objective 3.2-** The proportions of Veterans on care initiating CAB LA PrEP who used oral lead in (OLI) and proportion of those with direct to injection (DTI) will be calculated.

**Objective 3.3 and 3.4-** PrEP adherence and usage patterns will be described using median and interquartile range for continuous data as well as absolute and relative frequencies for categorical data. The percentage of days with access to oral PrEP and CAB LA PrEP will be described over the first 12 months after index PrEP initiation. Characteristics of individuals with and without delayed CAB LA injections as well as individuals with and without discontinuation will be compared using Pearson's chi-square tests for categorical variables and Mann-Whitney tests for continuous variables.

**Objective 3.5-** Incidence rates and confidence intervals for HIV testing, HIV diagnosis, STI testing/screening and STI diagnosis will be calculated using univariate Poisson regression. STI treatment prescription will be described using absolute and relative frequencies for categorical data.

**Objective 3.6-** For CAB LA PrEP users diagnosed with HIV, a timeline including details of oral PrEP prescriptions prior to CAB LA PrEP start, injections received, HIV tests performed, HIV treatment, viral load measurements, HIV drug resistance will be provided for each individual.

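### The CAB LA days-covered rule credits the first injection of a restart with 67 days, although the protocol treats a restart as a new two-injection initiation

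*Protocol*

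**What the plan says.** Protocol section 7.3.3, part b) on adherence to the CAB LA schedule, defines the proportion of days covered over the 12 months after initiation. It names the basis: "Coverage by LA PrEP will be determined based on the duration of days covered by the medication, according to the label". It then fixes two numbers. The first injection counts for 37 days (30 + 7). For all others: "Subsequent injections: coverage = 67 days (60 days of coverage + 7-day injection window". Each calendar day is counted once. There is no third value and no clause for an injection that starts a new series.

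Elsewhere the protocol recognises restarts:

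- For users whose first initiation was incomplete (more than 67 days without a second injection), 7.3.3 classifies a later series as "Complete versus incomplete reinitiation". It also tabulates the interval between the first two injections of that series, with 37 days or less as the first category.
- Table 3 labels a gap of 98–127 days in complete initiators "Long delay requiring reinitiation".
- For gaps over 127 days (discontinuation), the Objective 3.4 definitions count the "number of individuals resuming LA PrEP injections (additional CAB LA or LEN LA injections after discontinuation".

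Restarts can fall inside the measurement window, because Table 2 in section 7.1 ends the window only at: "Death, loss to follow-up (12 months after last clinical contact), study end, 12 months after index date whatever comes first". Discontinuation does not end it. Section 7.7.1.1 describes the result for both modalities: "The percentage of days with access to oral PrEP and CAB LA PrEP will be described over the first 12 months".

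**The concern.** Followed literally, the rule values the same step differently depending on when it happens. Take an initiation injection followed by the next injection 60 days later. At first start (day 0, next on day 60) the protocol credits 37 days and counts days 37–59 as uncovered. At a restart (day 200 after a 110-day gap, next on day 260) it credits all 60 days. No reason is given, and the protocol's own vocabulary describes both as the opening of a two-injection series.

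Days covered is a named CAB LA measure under Objective 3.3. Any excess runs in one direction, upwards, and falls on users with interrupted use, whom an adherence measure most needs to describe correctly. Section 7.8 plans an independent re-analysis, but with the same work instructions and code, so it may not bring the matter to light.

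**Working it through.** **The plan's own figures.** 30 + 7 = 37 days for the first injection and 60 + 7 = 67 for later ones. Both reproduce. The difference is 67 − 37 = 30 days.

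**Inputs from the protocol.** Coverage credits, single counting of days, and the incomplete-initiation limit (over 67 days) come from 7.3.3. The 98-day limit for reinitiation and the 127-day limit for discontinuation come from Table 3. Censoring comes from Table 2. The dates are the last eligible start, 30 June 2025, and study end, 31 December 2025 (7.1).

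**Assumed input.** A restart injection covers 37 days. The protocol does not state this value.

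**Excess per restart.** Let g be the days from the restart injection to the next injection, and r the days left in the window. Because days are counted once,

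excess = max(0, min(g, r, 67) − 37).

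| Gap g after restart (r at least 67) | Excess days | Points of 365 |
|---|---|---|
| 37 or less | 0 | 0 |
| 45 | 45 − 37 = 8 | 2.2 |
| 60 | 60 − 37 = 23 | 6.3 |
| 67 or more, or no further injection | 67 − 37 = 30 | 8.2 |

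If the label value were c days instead of 37, the cap would be 67 − c: 30 days at c = 37, 15 at c = 52, and 0 at c = 67.

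**Worked histories** (window days 0 to W − 1):

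- *Long delay.* Days 0, 30, 90, 200, 260, 320; W = 365. As written: 30 + 60 + 67 + 60 + 60 + 45 = 322 (88.2%). With reset, days 237–259 (23 days) are uncovered: 299 (81.9%).
- *Incomplete initiation.* Days 0 and 100 only; W = 365. 37 + 67 = 104 (28.5%) against 37 + 37 = 74 (20.3%).
- *Discontinuation.* Days 0, 30, 90, 220; W = 365. 30 + 60 + 67 + 67 = 224 (61.4%) against 30 + 60 + 67 + 37 = 194 (53.2%).
- *Shortest window.* The eligibility cut-off is set "to allow for at least 6 months of observation following PrEP initiation". From 30 June to 31 December 2025 is 184 days, the shortest window without a death. Days 0 and 68 only give 104/184 = 56.5% against 74/184 = 40.2%. The cap is then 30/184 = 16.3 points. This is an edge case.

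The cap applies per restart, not per person. As an extreme illustration, injections every 68 days (0, 68, 136, 204, 272, 340) never complete an initiation. They score 37 + 4 × 67 + 25 = 330 (90.4%) as written. If each failed reinitiation is also reset, they score 5 × 37 + 25 = 210 (57.5%).

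**Effect on the summary.** A person's first restart leaves at least 31 uncovered days even as written: 98 − 67 = 31 after a 67-day credit, or 68 − 37 = 31 after a 37-day credit. So no restarter exceeds (365 − 31)/365 = 334/365 = 91.5%, and the ceiling is lower in shorter windows. If more than half of users score above 91.5%, the reset cannot change the median.

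For scale only, assume that 2–10% of the 748 users (15–75 people) are affected, by 8–30 days each. The mean then shifts by 0.02 × 8/365 = 0.04 points to 0.10 × 30/365 = 0.82 points. The affected share has no source in the protocol, and 7.7.1.1 plans a median and interquartile range, not a mean.

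**The case against.** The strongest objection is that the error depends on a document nobody here can see. The protocol makes the label govern. If the label gave a restart injection 67 days, there would be no excess. That stands, and it is why the size is conditional. It does not remove the inconsistency: the protocol turned the label into two numbers, and a programmer will code those numbers. One could read 'first injection' as the first of each series, but the text does not say so.

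Second, for complete initiators part of the protocol's scheme fits the rule as written. Table 3 files a 98–127 day gap under late rather than discontinued. Time on CAB LA runs on until 127 days after the last injection. Maintenance injections are graded at 53–67 days, with no separate schedule after a long delay. Explicit categories for reinitiation appear only for incomplete initiators. This is fair, but the same Table 3 row says that reinitiation is required, so the scheme is not uniform. It also shows that changing the credit alone would create a new clash. In the first history above, Table 3 would grade day 260 as on time while days covered showed a 23-day lapse just before it. The fix must therefore include Table 3.

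Third, the planned output hardly moves, and interruptions are visible elsewhere: counts and durations of long delays, reinitiation intervals for incomplete initiators, and resumption after discontinuation. This also stands and limits the priority.

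A reader might infer that the rule biases a comparison of CAB LA with oral PrEP. The protocol does not support that. The study is descriptive, and its planned tests (7.7.1.1) compare groups within CAB LA only.

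**Conclusion.** The point holds in a limited form. The coverage rule as written gives a restart injection 67 days, while the protocol elsewhere treats a restart as a new two-injection initiation. If the restart credit is 37 days, days covered are overstated by 0 to 30 days per restart, at most 8.2 points of a 365-day window. The excess is zero when the second restart injection comes by day 37.

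The size rests on the 37-day value, which is inferred from the protocol's treatment of restarts and still has to be checked against the label. The share of users affected is unknown. The median probably moves little, and any effect falls on the lower part of the distribution. It would go too far to conclude that CAB LA adherence as a whole will be materially overstated: the protocol gives no restart frequency from which to show that. Correcting the rule is worthwhile, at low to medium priority.

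**What to change.** First confirm the coverage of a restart injection against the label that 7.3.3 names as governing. If it is 37 days, replace the two coverage lines in 7.3.3 with a rule such as:

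*The first injection of any initiation or reinitiation is credited 37 days; all other injections are credited 67 days. A reinitiation begins with the next injection after (a) an incomplete initiation or incomplete reinitiation, meaning more than 67 days without injection after a first or restart injection; (b) a gap over 97 days in a complete initiator; or (c) discontinuation.*

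Clause (a) has to include failed reinitiations. Otherwise a user who restarts on day 188 and is next injected on day 260 (a gap of 72 days) would again receive 67 days.

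Add a note to Table 3 that the second injection of a reinitiation is graded on the initiation schedule (23–37 days on time, 38–67 days late) rather than at 53–67 days, so that timing and days covered agree.

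If the label supports another value, use that value and state it. This concerns only how recorded injections are counted; no dosing rule is proposed.

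The cost is one rule, one table note, a label check and a few lines of code on data already extracted. The downside is slightly lower CAB LA days covered.

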**a) Oral PrEP**

- Discontinuation: any discontinuation, resumption of oral PrEP after discontinuation  
Two durations will be used to identify discontinuation of oral PrEP:
  - o Oral PrEP prescription not refilled within 30 days of the previous dispensing
  - o Oral PrEP prescription not refilled within 90 days of the previous dispensing
- Duration of oral PrEP use for the first period of use

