HIV testing is required to confirm that patients do not have HIV before starting PrEP (US CDC, 2025). People on daily oral PrEP need to see a health care provider every 3 months for repeat HIV tests, prescription refills, and follow-up. People using injectable PrEP need to see a healthcare provider every two or six months for an HIV test and the injections, depending on which option they chose (HIV.gov, 2025 a). Screening for other sexually transmissible infections (STIs) is an important part of PrEP clinical follow-up and monitoring (Jenness, 2017). It allows for early detection and treatment of STIs that would otherwise go undetected.

Understanding patterns of PrEP use is key to optimizing its effectiveness in HIV prevention and improve clinical practice and public health benefits. Analyzing how people use PrEP can help design effective strategies for uptake, adherence and continuation leading to better public health outcomes. This study will provide real-world evidence on PrEP use patterns, HIV testing and STI screening in individuals on either oral or LA PrEP, as well as potential incident HIV diagnoses on PrEP.

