**Objective set 2- Veterans in care with no evidence of HIV infection who are not on PrEP but could benefit from PrEP**

- 2.1- Describe the characteristics of Veterans in care who are not on PrEP but could benefit from PrEP
- 2.2- Estimate HIV testing and diagnoses rates, as well as rates of STI screening/testing rates, STI diagnoses among Veterans in care who are not on PrEP but could benefit from PrEP, over a 12-month period of follow-up

**Objective set 3- Veterans on care with no evidence of HIV infection who initiate PrEP (oral or CAB LA injectable) during the study period**

- 3.1- Describe the population of Veterans in care who initiated oral PrEP or CAB LA injectable PrEP, including their demographic, clinical and sexual behavioral characteristics, the year of PrEP initiation and the duration of follow-up
- 3.2- Describe the proportions of Veterans on care initiating CAB LA PrEP who used oral lead in (OLI) and proportion of those with direct to injection (DTI).
- 3.3- Describe adherence to oral and CAB LA injectable PrEP
- a) Oral PrEP use only: number days oral PrEP supplied divided by number of days in observational period
  - b) CAB LA injectable PrEP
    - Number of days covered by CAB LA PrEP divided by the number of days in the observation period
    - Timing and completion of initiation injections
    - Among complete initiators with at least one maintenance injection, timing of maintenance injections: all on time, any late injection (short delay not requiring reinitiation, long delay requiring reinitiation)
    - Baseline characteristics of users with all injections on time versus users with any late maintenance injection
- 3.4- Describe patterns of PrEP use
- a) Oral PrEP:
    - Discontinuation: any discontinuation, resumption of oral PrEP
    - Duration of oral PrEP use for the first period of use
  - b) CAB LA injectable PrEP
    - Discontinuation: any discontinuation, resumption of long-acting injections (with CAB LA injectable or LEN LA injectable) or oral PrEP after discontinuation
    - Oral bridging between discontinuation of CAB LA injections and resumption of CAB LA injections
    - Duration of CAB LA PrEP use in months

- first period of use
  - cumulative use throughout the study period in case of discontinuation followed by resumption of CAB LA PrEP injection(s)
  - Baseline characteristics of users discontinuing CAB LA PrEP versus users who did not discontinue

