**a) Oral PrEP coverage in the 12 months following initiation**

PrEP dispensing is considered as a proxy for PrEP use. The number of dispensing events will be described.

The number of pills dispensed/days covered per dispensing event will be calculated.

Proportion of days of access to oral PrEP in the 12 months following index PrEP initiation

Follow-up (FU) will be censored at first of:

- 12 months after index date
- Loss to follow-up
- Death
- Study end

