    - Incidence proportion and incidence rate of HIV testing between the start of PrEP and the first discontinuation
    - Timing of HIV tests:
      - Oral PrEP: on-schedule testing defined as receiving an HIV test  $\leq 7$  days before/at start, and 3 months (76-104 days) after each test
      - CAB LA PrEP: on-schedule testing defined as receiving an HIV test

≤7 days before/at first injection, and 14 days prior each subsequent injection

- HIV diagnosis: incidence proportion and incidence rates between index date and the 1st discontinuation
- STI testing/screening
  - Assessed during the first period of PrEP use (oral or injectable)
    - Incidence proportion and incidence rate for STI testing/screening for
      - Gonorrhea
      - Chlamydia
      - Syphilis
      - Chancroid
      - Lymphogranuloma venereum
      - *Mycoplasma genitalium*
      - Hepatitis B virus (HBV)
      - Hepatitis C virus (HCV)
      - Genital Herpes (HSV-1, HSV-2)
      - Trichomoniasis
      - Genital Human papilloma virus (HPV) including warts
    - Interval between the first 2 tests for gonorrhea, chlamydia, syphilis done during the first period of PrEP use
      - Testing 3 months (76-104 days) after last test
      - Testing 6 months (168-196 days) after last test
      - Testing 12 months (351-379 days) after last test
- STI diagnoses
  - New diagnosis of STI as noted in medical record or positive test result
  - STI diagnoses for
    - Syphilis
    - Gonorrhea
    - Chlamydia
    - Chancroid
    - Lymphogranuloma venereum
    - *Mycoplasma genitalium*
    - Hepatitis B virus (HBV)
    - Hepatitis C virus (HCV)
    - Genital Herpes (HSV-1, HSV-2)
    - Trichomoniasis
    - Genital Human papilloma virus (HPV) including warts
- Relevant prescription for a selected list of STIs  
 Proportion of STI diagnosis with a prescription within 14 days following diagnosis as follows:
  - Syphilis: benzathine penicillin G, aqueous crystalline penicillin G, procaine penicillin G + probenecid, doxycycline
  - Gonorrhea: ceftriaxone, ceftriaxone + doxycycline, gentamicin + azithromycin,

- cefixime, cefotaxime
- Chlamydia: doxycycline, azithromycin, levofloxacin, amoxicillin
- Chancroid: azithromycin, ceftriaxone, ciprofloxacin, erythromycin base
- Lymphogranuloma venereum: doxycycline, azithromycin, erythromycin base
- *Mycoplasma genitalium*: doxycycline + azithromycin, doxycycline + moxifloxacin
- Trichomoniasis: metronidazole, tinidazole

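### Both oral PrEP discontinuation thresholds run from the dispensing date and ignore days supplied, so with fills of about 90 days the 30-day rule counts continuously supplied users as stopped and the 90-day rule allows no grace

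*Protocol*

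**What the plan says.** Section 7.3.3, Patterns of PrEP use (Objective 3.4), a) Oral PrEP, states: "Two durations will be used to identify discontinuation of oral PrEP". The two are "Oral PrEP prescription not refilled within 30 days of the previous dispensing" and "Oral PrEP prescription not refilled within 90 days of the previous dispensing". No discontinuation date is given for oral use.

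Other parts of the protocol bear on this rule:

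- Section 5 gives the expected refill rhythm: "People on daily oral PrEP need to see a health care provider every 3 months for repeat HIV tests, prescription refills, and follow-up".
- Objective 3.3a in Section 6 measures oral adherence as "number days oral PrEP supplied divided by number of days in observational period", and Section 7.3.3 adds: "The number of pills dispensed/days covered per dispensing event will be calculated".
- Objective 3.5 outcomes in Section 7.3.3 stop at the first discontinuation, for example "Incidence proportion and incidence rate of HIV testing between the start of PrEP and the first discontinuation". On-schedule oral HIV testing is set at "3 months (76-104 days) after each test".
- For CAB LA, Section 7.3.3 counts 67 days of coverage per injection after the first and dates discontinuation 127 days after the last injection.

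**The concern.** A refill gap shows that a user has stopped only if it is measured against the supply in hand. Measured from dispensing, the same threshold is strict for a large fill and lenient for a small one. A Veteran could have 100% of days covered under Objective 3.3a and still be a discontinuer at day 30 under Objective 3.4a, and then a resumer at the next routine refill.

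The discontinuation, resumption and duration results of Objective 3.4a are at stake. So is the oral follow-up used for HIV and STI testing and diagnosis during the first period of use in Objective 3.5, which is reported by PrEP modality.

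**Working it through.** The protocol gives no figure for oral discontinuation, so there is nothing to reproduce. The check applies the stated rule to simple refill histories.

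**Inputs.** Thresholds of 30 and 90 days from dispensing, and the CAB LA figures of 67 and 127 days, are from Section 7.3.3. The 3-month refill interval is from Section 5. Days' supply per fill is not stated. I assume 30, 60 or 90 days and show all three.

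**Step 1: grace after supply ends.** Grace = threshold − days supplied.

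| Fill | 30-day rule | 90-day rule |
|---|---|---|
| 30 days | 30 − 30 = 0 | 90 − 30 = 60 |
| 60 days | 30 − 60 = −30 | 90 − 60 = 30 |
| 90 days | 30 − 90 = −60 | 90 − 90 = 0 |

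CAB LA has 127 − 67 = 60 days after its coverage ends.

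**Step 2: regular refill histories over 365 days.** Unused supply is carried forward. Discontinuation is placed on the day the rule is met, which is my assumption because the protocol gives no date.

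| Fill / refill interval (days) | Days covered | 30-day rule | 90-day rule | Either gap counted from end of supply |
|---|---|---|---|---|
| 30 / 30 | 100% | no | no | no |
| 30 / 31 | 97.0% | day 30 | no | no |
| 60 / 60 | 100% | day 30 | no | no |
| 90 / 76, 83 or 90 | 100% | day 30 | no | no |
| 90 / 91 | 98.9% | day 30 | day 90 | no |
| 90 / 92 | 98.4% | day 30 | day 90 | no |
| 90 / 104 | 88.5% | day 30 | day 90 | no |

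**Step 3: how often a 3-month refill passes day 90.** I took every start date from 1 January 2021 to 31 December 2024 (1,461 dates), each with four successive calendar 3-month gaps: 1,461 × 4 = 5,844 gaps. Of these, 345 last 89 days, 869 last 90, 1,245 last 91 and 3,385 last 92. The share above 90 days is (1,245 + 3,385) / 5,844 = 4,630 / 5,844 = 79%. All 1,461 start dates give at least one gap above 90 days within the year.

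The protocol's own 3-month window for HIV tests, 76 to 104 days, spans 29 days. Of these, 14 (91 to 104) lie beyond day 90: 14 / 29 = 48%. All 29 lie beyond day 30.

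**Step 4: reach into Objective 3.5.** If the 30-day definition governed and discontinuation were dated at day 30, the first period would close 76 − 30 = 46 days before the first on-schedule repeat test window opens, for a test done at the start. The protocol settles neither condition, so this is the extreme case and not a stated result.

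**The case against.** **Two definitions are planned.** Under the 90-day rule, a 90-day fill refilled by day 90 is classed correctly, and 30- and 60-day fills have real grace. This stands. The 90-day error comes only from the lack of grace and is not universal. It does not rescue the 30-day results, which are also to be produced.

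**The 90-day fill is an assumption.** Section 5 gives a visit and refill interval, not a quantity. With 30-day fills refilled by day 30, neither rule misclassifies anyone. A reader might infer that the oral results would mostly reflect fill size. The documents do not support that, because they do not give the distribution of fill sizes.

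**The effect on Objective 3.5 is not fixed.** A reader might infer that all oral follow-up there shrinks to 30 days. The protocol names neither the governing definition nor the oral date, so the shortening cannot be sized. Shorter follow-up biases a person-time rate only if the rate changes over time. That is plausible for testing, but the documents do not quantify it. The incidence proportions that are also planned depend directly on length of follow-up.

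**Refills at day 91 or 92 are real lapses.** On a 90-day fill they leave 1 or 2 days uncovered, so these users are not fully supplied. That is correct, but so short a lapse is a poor marker of having stopped PrEP.

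**The study is descriptive.** It plans no test between modalities. That limits the consequences but does not make the descriptive oral estimates right.

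The authors may have meant the end of the previous supply. The text does not say so, and a programmer would follow the text.

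**Conclusion.** The point holds in a bounded form. Counting from dispensing makes the 30-day definition wrong for any fill longer than 30 days that is refilled as it runs out. With 90-day fills, every continuously supplied user is classed as discontinued about 60 days early. Under the 90-day definition a 90-day fill has no grace, and 79% of calendar 3-month gaps overrun it. A 30-day fill likewise has no grace under the 30-day definition.

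The result for 90-day fills rests on an assumed supply that fits the 3-month refills in Section 5 but is not stated. Oral discontinuation, resumption and first-period duration in Objective 3.4a are affected, and they conflict with the days-supplied logic of Objective 3.3a. Oral follow-up during the first period of use in Objective 3.5 is affected to an unknown extent. Objective 3.3a adherence, which uses a fixed 12-month window, and the STI rates for the 6 months before initiation are not affected.

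**What to change.** In Section 7.3.3, a) Oral PrEP:

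1. Count the 30- and 90-day gaps from the end of supply on hand, carrying unused supply forward. Use the days covered per dispensing event that the protocol already plans to calculate.
2. State the date assigned to oral discontinuation.
3. State which of the two definitions ends the first period of use in Objective 3.5.
4. Use one dating convention for both modalities: either both at the end of coverage or both at the end of the grace period. Dating oral use at run-out while CAB LA stays at 127 days after the last injection would leave CAB LA with 60 days of person-time beyond coverage and oral with none.

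The cost is a few sentences and no new data. The downside is later detection. After a final 90-day fill, the longer definition needs 90 + 90 = 180 days of follow-up instead of 90, so a few more oral users will be censored at study end.
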